5.7.2 Termination of the Trial by the Sponsor

Harbour BioMed reserves the right to terminate the trial or a study site for any reason listed below at any time:

- The overall enrollment or enrollment at a study site does not meet the target;
- Any efficacy/safety information that can significantly affect the implementation of this trial and does not support the initial positive benefit-risk assessment;
- Violations against GCP, CTP or the contract and interfere with normal implementation of the trial.

If the trial is terminated, investigators/study sites will be compensated reasonably (except in the third case listed above).

6 LABELING, PACKAGING, STORAGE, DISPENSE AND RETURN OF STUDY DRUGS

6.1 Subject Information

The packaging for the study drugs needs to meet the study requirements. Study staffs will use IWRS to assign subjects to treatment groups, dispense study drugs, and manage the drug dispense. The study drugs need to be packaged according to the drug package plan made by the Sponsor. A unique personal identification number (PIN) must be assigned to the persons who access the IWRS system. These personnel must use the PIN allocated to them to enter the system and not share their PIN with anyone else.

6.2 Product Description

Study drug will be supplied as a sterile, clear, colorless liquid solution containing 0.25% API (HBM9036) in 0.5 mL low-density polyethylene (LDPE) unit dose vials with a fill volume of approximately 0.25 mL. Each mL of the 0.25% solution contains 2.5 mg of the API. In addition to HBM9036, the components of the drug solution are: sodium chloride (tonicity adjusting agent), citric acid monohydrate (buffering solution), sodium hydroxide solution and hydrochloric acid 1% (both for pH adjustments), and sterile water for injection as a solvent.

The placebo solution consists of all components of the drug product solution except for HBM9036.

6.3 Packaging and Labeling Information

Batch #(ID for tracing packaging ID)	Storage Conditions
Drug #	Protocol #
Composition ID #	Regulatory Requirements
Specification and Formulation	Sponsor's Contact Information

ID= identification number; #=number

6.4 Emergent Unblinding of Treatment Assignment

The IWRS should be used to unblind subjects and to unmask drug identity. When the Investigator contacts the system to unblind a subject, he/she must provide the requested subject identifying information and confirm the necessity to unblind the subject. Harbour BioMed will not provide a disclosure envelope with the clinical supplies.

The Investigator or treating physician may unblind a subject's treatment assignment only **in the case of an emergency**, when knowledge of the study treatment is essential for the appropriate clinical management or welfare of the subject.

Whenever possible, the Investigator must first discuss options with the clinical research associate (CRA) or appropriate study personnel before unblinding the subject's treatment assignment. If this is impractical, the Investigator must notify the Sponsor as soon as possible,

but without revealing the treatment assignment of the unblinded subject, unless that information is important for the safety of subjects currently in the study. The date and reason for the unblinding must be recorded in the appropriate data collection tool.

6.5 Storage Requirements

HBM9036 and placebo solution must be refrigerated (2-8°C). Subjects will be told to store HBM9036 and placebo solution in the fridge (at 2-8°C).

6.6 Preparation and Dispensing of Study Treatments

Study drugs will be packaged and labeled into study kits. Both sterile drug and placebo solutions are packaged in disposable 0.5 mL LDPE vials with a dose of about 50 µL per drop. Each two vials are placed in a nitrogen-filled aluminum foil bag, providing the dose for one day. Each study kit contains enough medications until the next study visit.

For the screening visit (Visit 1), drugs will be dispensed according to the schedule of assessments and visit window.

For the treatment period, drugs are distributed according to requirements of each study visit considering visit window.

Subjects will be suggested to put 1 vial of HBM9036 or placebo solution at room temperature 1±0.5 hours before drug administration.

At study sites, all IPs must be stored safely under the storage conditions specified in the protocol and only accessed by qualified personnel designated by the study site. All IPs must be stored and managed in accordance with local regulations, ICH GCP and study procedures, and inventory must be carefully and accurately recorded.

6.7 Treatment Compliance

Subjects will be required to record the use of study drugs in their diaries every day which will be used for evaluation of subject's treatment compliance. Drug usage of 80% to 125% will be evaluated as good compliance.

Treatment compliance will be calculated as: $(\text{actual drug use} / \text{planned drug use}) \times 100\%$. The actual drug use is the amount of drug used by subjects between the drug dispensing and next study visit (based on the records of drug use reviewed by the Investigator); and the planned drug use is calculated as $(\text{daily drug use specified in the protocol}) \times (\text{the optimum interval between two study visits})$. The decrease in drug dose caused by the treatment interruption or dose decrease because of AEs is not considered as poor compliance.

6.8 Drug Accountability/Return of Study Drugs

The study drug is not allowed to be used by investigators in any case, unless specified in the protocol.

A staff will be authorized by the study site to receive, safely and appropriately manage and preserve and store study drug in a safe place. The study drug can be inspected only by authorized staff. The storage conditions of the study drugs should be observed, monitored and recorded carefully, and study drugs should be distributed according to the protocol. Investigators or other authorized personnel will be responsible for accurately recording the amount of drugs received from Harbour BioMed, delivered to subjects, returned by subjects, and the amount of drugs remaining at the end of study. The study drug should be disposed according to Good Supply Practice for Pharmaceutical Products. In case of any problems requiring special or protective handling, the clinical research associate should be contacted. All study drugs, including partially used or empty containers, must be returned at the end of the study as required by Harbour BioMed.

Staff at study sites will check the records for drug accountability together and the records will be monitored by the Sponsor's CRA regularly.

Before the completion of all pre-dose evaluations and confirmation of subjects' eligibility for randomization/participation in the study, authorized staff will not be allowed to open the package of study drug. Any action that violates the requirements listed above must be discussed with the CRA.

All used drug package used by subjects and unused study drugs will be collected. The study drugs used by subjects will be stored in safety locker at room temperature before being returned to Harbour BioMed or its authorized personnel.

Note: the used drug package and unused study drugs should be stored separated from the study drugs not dispensed.

All complaints related to product quality (including package problems) must be reported to Harbour BioMed using the Product Complaint Form in the folders of each site. Harbour BioMed will contact study sites to assess the nature of the complaints and decide the further measures that need to be taken.

7 SAFETY

7.1 Safety Assessments

The safety of the investigational product will be evaluated according to adverse reactions and all ophthalmologic findings (see details in Section 3.3).

7.1.1 Medical/Surgical History and Ophthalmologic Examination

See Section 8 Study Plan and Section 3.3 Safety Endpoints for detailed information.

7.1.2 Pregnancy Test

Urine pregnancy tests will be conducted for premenopausal women without surgical contraception in the laboratories of all study sites at Visit 1 (screening visit) and Visit 6 (Week 8) or at study discontinuation/withdrawal.

7.1.3 Drop Tolerance Assessed Using Ora Calibra[®] Drop Tolerance Scale and Ora Calibra[®] Drop Tolerance Questionnaire

Drop tolerance will be assessed using the Ora Calibra[®] Drop Tolerance Scale and Ora Calibra[®] Drop Tolerance Questionnaire at each study site at Visit 2.

7.2 Adverse events

7.2.1 Definition of AEs

An AE refers to all untoward medical occurrence after the use of an IP. An AE can be any sign, symptom or abnormal clinical laboratory results, but may not necessarily have a causal relationship with the IP.

An AE includes, but are not limited to:

- Any symptom or condition (medical history) not reported previously by subjects;
- An aggravation of existing symptoms or conditions;
- Significantly increased frequency or intensity of existing events or conditions;
- Conditions discovered or diagnosed for first time after the administration of the investigational product, even if they may already exist prior to initiation of the study.

An AE does not include:

- Routine medical or surgical procedures caused by non-disease factors (e.g., plastic surgery, endoscopy, biopsy);
- Planned surgical procedures before enrollment (e.g., cataract surgery) or hospitalization due to social factors (e.g., medical insurance);

- Overdose of either study drug or concurrent medication without any clinical signs or symptoms;
- Non-clinically significant abnormal laboratory values. (If accompanied by signs/symptoms, the signs or symptoms are considered an AE.).

7.2.2 Collection of Adverse Events

Adverse events that occur between the time subject signs the ICF for the study and the time when that subject is randomized will be summarized as medical history and not as a treatment-emergent adverse event unless the event meets the definition of an SAE or AE related to protocol specific procedures.

Adverse events that occur between the time when subject is randomized and last visit should be reported through CRF. All SAEs should be reported to Harbour BioMed within 24 hours of awareness.

Any SAE between last visit and study completion that has a causal relationship with investigational product should be immediately reported to Harbour BioMed and recorded in CRF.

Post-study AE/SAE that investigators judge its occurrence related to investigational product should be reported to Harbour BioMed PV through spontaneous reporting.

7.2.3 Assessment of Adverse Events

The Investigator should immediately record and report all AEs via CRF and AE report forms during the study. All SAEs (see Section 7.2.7) must be reported to Harbour BioMed or designee within 24 hours after the Investigator recognizes/classifies the event as an SAE.

When a SAE occurs, the subject may be discontinued from the treatment after investigators have thorough discussion with medical monitors.

The Investigator will categorize the severity of each AE according to the following criteria:

Mild: Associated with no limitation of daily activities or only slight discomfort; generally not requiring change or interruption of study drugs; and/or not needing therapeutic intervention;

Moderate: Associated with limitation of daily activities or obvious discomfort; generally requiring change or interruption of study drugs; and/or requiring therapeutic intervention;

Severe: Associated with inability of subject to carry out daily activities or obvious discomfort; considered to be life-threatening; resulting in significant disability or incapacity; and requiring therapeutic intervention.

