3.3 Safety Evaluation

- Incidence and severity of ocular AEs
- Incidence and severity of non-ocular AEs

- BCVA at each visit
- Slit-lamp bio-microscopic results at each visit
- Evaluation of tolerance (at Visit 2) by Ora Calibra[®] Drop Comfort Scale and Ora Calibra[®] Drop Comfort Questionnaire
- Intraocular pressure (at Visits 1 and 6)
- Fundus photography (at Visits 1 and 6)

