Severity of an adverse event is defined as a qualitative assessment of the degree of intensity of an adverse event as determined by the investigator or reported to him/her by the patient/subject. Summaries of TEAEs by maximal severity will be presented for ocular AEs and non-ocular AEs separately. The number of subjects with any TEAEs (along with percentages) will be tabulated by SOC and PT within each SOC by treatment group. To count the number of subjects with any TEAEs, if a subject has multiple TEAEs coded to the same PT within the same SOC, the subject will be counted once under the maximal severity. All probable, unclassified, and definite TEAEs are considered as treatment-related TEAEs. All AEs will be presented in a subject listing.

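### Protocol 7.2.3 gives no usable boundary between Moderate and Severe adverse events, so the Severe grade may be under-used or applied inconsistently in the planned severity tables

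*Protocol*

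**What the plan says.** Protocol 7.2.3 instructs the investigator to grade every adverse event (AE) by three definitions.

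- **Mild** covers no limitation of activities or only slight discomfort, and goes on "generally not requiring change or interruption of study drugs; and/or not needing therapeutic intervention".
- **Moderate** is "Associated with limitation of daily activities or obvious discomfort", and goes on "generally requiring change or interruption of study drugs; and/or requiring therapeutic intervention".
- **Severe** opens "Associated with inability of subject to carry out daily activities or obvious discomfort" and goes on "considered to be life-threatening; resulting in significant disability or incapacity; and requiring therapeutic intervention".

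Protocol 7.2.7 defines a serious AE (SAE) by a list in which any one criterion is enough. Two of the criteria are immediate risk of death, and persistent or significant incapacity or a major disruption of ordinary functioning.

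Protocol 3.3 lists "Incidence and severity of ocular AEs" as a safety evaluation, with a matching item for non-ocular AEs. SAP 7.1 states: "Summaries of TEAEs by maximal severity will be presented for ocular AEs and non-ocular AEs separately". A subject with several events under one preferred term is counted once, at the highest grade. SAP 7.1 also describes severity in general terms, as a qualitative judgement of intensity made by the investigator or reported by the subject. It sets no grade boundaries.

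**The concern.** Two features of the Severe definition stand out beside the other two grades. First, its list closes with 'and' where theirs use 'and/or', and two of its elements, threat to life and disability or incapacity, closely match seriousness criteria in Protocol 7.2.7. Severity (how intense an event is) and seriousness (what its outcome or risk is) are normally recorded as separate attributes, and here the top severity grade borrows from seriousness. Second, obvious discomfort appears in both Moderate and Severe.

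At stake is the meaning of the Severe column. Safety is the secondary objective (Protocol 2.2), and the trial is meant to inform Phase III (Protocol 2.1; SAP 1.1). The events of interest for an eye drop are mainly ocular. In the US Phase II study (Protocol 1.4.2), 8 subjects on 0.25% and 1 on placebo had drug-related ocular treatment-emergent AEs (TEAEs), and 8 subjects on active drug withdrew for allergic conjunctivitis. If the top grade is rarely available for such events, or is used differently from site to site, a summary saying that all TEAEs were mild or moderate would carry less information than it appears to.

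**Working it through.** The plan states no figure on this point and no arithmetic applies. The check is to split the Severe definition into its elements and test example events under each reading.

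**Elements of Severe (Protocol 7.2.3)**

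1. Inability to carry out daily activities, or obvious discomfort
2. Life-threatening
3. Significant disability or incapacity
4. Requiring therapeutic intervention

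**Reading L (literal):** the closing 'and' makes all four necessary. The use of 'and/or' in the other two grades of the same scale supports this reading.

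**Reading A (alternatives):** the semicolons separate alternatives and any one element is enough.

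| Example event | Reading L | Reading A |
|---|---|---|
| Eye pain that briefly stops daily activities; treated; judged non-serious | Fails 2 and 3, so not Severe; falls to Moderate | Meets 1 and 4, so Severe; also fits Moderate |
| Obvious discomfort; treated; activities continue | Fails 2 and 3; Moderate | Meets 1 and 4, so Severe; also fits Moderate |
| Incapacitating and so serious under 7.2.7; treated; no risk to life | Fails 2, so not Severe | Meets 1, 3 and 4, so Severe; also fits Moderate |
| Slight discomfort; no limitation; untreated | Mild | Mild |

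The first and third events fit Moderate because inability to carry out activities is at least a limitation of them, and because Moderate also includes therapeutic intervention.

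**What follows**

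- Under reading L, every Severe event is life-threatening and therefore an SAE. A non-serious event cannot be Severe, and the third row shows that some serious events cannot be either. The shared discomfort phrase does no harm under this reading, because element 2 already separates the grades.
- Under reading A, threat to life is not required and Severe is not restricted to SAEs. But obvious discomfort and therapeutic intervention each appear in both grades, so a treated event with obvious discomfort satisfies both definitions.
- Under both readings Mild remains distinguishable from Moderate: slight against obvious discomfort, and no limitation against limitation.

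The first two rows are the practical problem. They differ in functional impact, yet reading L puts both in Moderate and reading A lets both be either grade. Two investigators applying 7.2.3 in good faith could record different grades for the same event, and the maximal-severity rule in SAP 7.1 carries that difference into the subject counts.

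**The case against.** The strongest reply is that this is loose drafting with little practical effect. Investigators commonly grade by intensity, and SAP 7.1 describes severity that way, which leaves room for a non-life-threatening event to be recorded as Severe. The tables only report the grade that was recorded. Important events are also captured without the grade: SAEs and serious TEAEs, discontinuations due to AEs, and treatment-related ocular TEAEs (SAP 7 and 7.1), and visual acuity, slit-lamp, intraocular pressure and fundus results (SAP 7.2). The US Phase II study reported only mild or moderate TEAEs, so few Severe events may occur here whatever the wording.

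Much of this stands, and it limits the importance of the point. It does not remove it. The SAP description has no boundaries and does not replace the criteria that Protocol 7.2.3 tells investigators to apply; at present the two documents describe severity differently. The US result is only suggestive, because the documents do not say which grading scale that study used.

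A reader might also infer that no non-serious event could ever be Severe, however disabling. The documents do not support that form. It depends on the literal reading, and a sufficiently incapacitating event is already serious under 7.2.7.

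**Conclusion.** The point holds in a limited form and is of low importance. The Moderate/Severe boundary in Protocol 7.2.3 is unsound whichever way it is read: one reading ties Severe to seriousness, the other makes it overlap Moderate. Severe may therefore be under-used or graded inconsistently in the maximal-severity tables.

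Two stronger conclusions are tempting. One is that the severity tables cannot grade ocular AEs correctly. That goes too far, because only one boundary is affected and investigators may in practice grade by intensity. The other is that Severe is both confined to life-threatening events and overlapping with Moderate. Those two faults need opposite readings of the same sentence and cannot both operate at once.

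The number of AEs affected cannot be sized from the documents. The conclusion assumes that investigators follow 7.2.3 as written and that no eCRF guidance, which is not among these documents, resolves the wording. The efficacy analyses are untouched.

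**What to change.** In Protocol 7.2.3 and the eCRF completion guidance:

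- Remove the life-threatening and disability/incapacity terms from Severe. They stay in the SAE definition in 7.2.7.
- Remove obvious discomfort from Severe, leaving it in Moderate.
- Make inability to carry out daily activities (Severe) versus limitation of them (Moderate) the discriminator.
- Do not let the need for therapeutic intervention qualify an event as Severe on its own. Moderate already uses that criterion, so a stand-alone version would recreate the overlap.

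In SAP 7.1, replace the general description of severity with a reference to the revised protocol scale, so that both documents use one definition.

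The cost is about one sentence of protocol text with the matching eCRF and SAP wording. The severity distribution may look somewhat less favourable, because non-serious events that prevent daily activities could then be graded Severe.

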7.2.4 Causality

The relationship of each AE to the administration of study drug will be assessed by the Investigator after careful consideration, and according to the following guidelines:

Definitely: A reaction that follows a reasonable temporal sequence from administration of study drug; that follows a known or expected response pattern to the study drug; it disappears or decreases on cessation or reduction in study drug dose; and/or it reappears or worsens when the study drug is administered;

Probably: A reaction that follows a reasonable temporal sequence from administration of study drug; that follows a known or expected response pattern to the study drug; but it could also be reasonably explained by other factors such as underlying disease, complications, concomitant medications or treatments;

Possibly unrelated: A reaction that does not follow a reasonable temporal sequence from administration of study drug; that does not follow a known or expected response pattern to the study drug; it could be reasonably explained by other factors such as underlying disease, complications, concomitant medications or treatments;

Unrelated: A reaction that follows a reasonable temporal sequence from administration of study drug; that follows a known or expected response pattern to the study drug; it disappears or decreases on cessation or reduction in study drug dose; and/or it reappears or worsens when the study drug is administered;

Inaccessible: A reaction for which current data is too insufficient to assess its relationship with the study drug.

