1.4.2 Phase II Study

The Phase II, dose range, and proof-of-concept study of HBM 9036 was completed in the US. This was a multicenter, randomized, double-blinded, placebo-controlled study. Subjects were randomly assigned to one of three treatment groups (HBM9036 Ophthalmic Solution 0.10%, 0.25% or placebo) to receive topical ophthalmic drops administered bilaterally BID. The study lasted for 8 weeks and included 6 visits. Although the primary sign of fluorescein staining at Visit 6 pre-CAE was not met with an ANCOVA analysis, analysis of the change in fluorescein staining score pre-CAE to post-CAE as well as post-CAE showed significant treatment differences from baseline starting as early as Visit 4 (Day 15) in total corneal and superior staining, and these significant treatment differences became consistent at Visit 5 (Day 29) and Visit 6 (Day 57). Significant improvements in burning and itching as assessed by the VAS were seen in favor of the HBM9036 0.25% group as early as Visit 4 (Day 15) and continued to Visit 6 (Day 57). Significant improvement was observed in total OSDI score in the HBM9036 0.25% treatment group compared with placebo group.

In the safety population, 44 (29.3%) subjects reported 64 AEs. Of them, 37 (24.7%) subjects reported 51 treatment-emergent adverse events (TEAEs), including 26 ocular TEAEs and 25 non-ocular TEAEs. All TEAEs were of mild or moderate severity. A total of 16 (10.7%) subjects reported at least one ocular TEAE related to the study drug. Of them 7 subjects were treated with HBM9036 (HL036) 0.10%, 8 subjects were treated with HBM9036 0.25%, and 1 subject was treated with placebo. The most common unexpected ocular TEAEs related to the study drug were installation site pain and allergic conjunctivitis. No deaths or SAEs were reported in the study. A total of 8 subjects withdrew from the study due to allergic conjunctivitis: 3 subjects were from HBM9036 (HL036) 0.10% group and 5 subjects were from HBM9036 (HL036) 0.25% group. No change of clinical significance was reported for other safety endpoints.

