7.2.7.4 Safety Reports to the Health Authority

The Investigator must report the SAE to National Medical Products Administration (NMPA) and its local affiliates, and National Health Commission (NHC) within 24 hours after he receives the SAE information. The report also needs to be sent to the pharmacovigilance team at Harbour BioMed. The follow-up report should be reported within the same time frame as the initial SAE report.

Harbour BioMed or its representatives will submit a safety report to NMPA and NHC, for any suspected adverse reaction that is both serious and unexpected (SUSAR) within the appropriate time frame (initial report: 7 days for death or life-threatening case, 15 days for other SUSAR; follow-up report: 8 days for death or life-threatening case, 15 days for other SUSAR). Other SAEs will be reported in annual report.

Harbour BioMed or its representatives will send the investigators who are participating in the clinical studies sponsored by Harbour BioMed the copies of each safety report submitted to NMPA. Safety reports must be submitted to the appropriate EC as soon as possible. Documentation of the safety report submitted to the EC must be retained.

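### Both positive causality grades require a known response pattern, so a plausibly timed reaction of a new type has no related grade

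*Protocol*

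**What the plan says.** Protocol 7.2.4 lists five grades, which it introduces as guidelines for the investigator's assessment.

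- *Definitely*: plausible timing; then "that follows a known or expected response pattern to the study drug; it disappears or decreases on cessation or reduction in study drug dose". Alternatively or in addition, the event returns or worsens on dosing.
- *Probably*: plausible timing; then "that follows a known or expected response pattern to the study drug; but it could also be reasonably explained by other factors". Examples given include the patient's other illness or medication.
- The third grade begins "Possibly unrelated: A reaction that does not follow a reasonable temporal sequence from administration of study drug". It adds that no known pattern is followed and that other factors could explain the event.
- The fourth begins "Unrelated: A reaction that follows a reasonable temporal sequence from administration of study drug; that follows a known or expected response pattern" and goes on to repeat the whole text of *Definitely*.
- The fifth is "Inaccessible: A reaction for which current data is too insufficient to assess its relationship with the study drug".

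Protocol 7.2.7.1 makes the investigator's causality a minimum item of the first SAE report. Protocol 7.2.7.4 has the sponsor send the authorities an expedited report for "any suspected adverse reaction that is both serious and unexpected (SUSAR) within the appropriate time frame" (7 days for fatal or life-threatening cases, 15 days for others). Other SAEs go into the annual report. No causality grade is named there.

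SAP 7.1 states: "All probable, unclassified, and definite TEAEs are considered as treatment-related TEAEs". It plans separate tables of treatment-related ocular and non-ocular TEAEs.

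**The concern.** Whether a drug caused an event and whether that kind of event was already known are separate questions. Section 7.2.4 merges them: prior knowledge of the event type is a condition of both grades that affirm a link. The SUSAR rule works the other way, since it is meant for reactions that are suspected and also unexpected. A site that applies the grade text strictly has no positively related grade for exactly the kind of event that rule is written for.

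Two outputs depend on the grade. One is the pair of treatment-related TEAE tables. The other is the sponsor's decision between a 7- or 15-day report, which is also copied to participating investigators, and the annual report. There is no data monitoring committee (7.2.11), so recognition of a new reaction rests with the investigators and the sponsor.

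**Working it through.** No arithmetic applies, and there is no figure in the plan to reproduce. The check is to run one event through the rules as printed.

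**Test event.** Well documented; starts soon after dosing; of a type not described before.

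| Grade (7.2.4) | Condition that decides it | Fits? |
|---|---|---|
| Definitely | needs a known pattern | no |
| Probably | needs a known pattern | no |
| Possibly unrelated | needs implausible timing | no |
| Unrelated (as printed) | needs a known pattern | no |
| Inaccessible | needs insufficient data | no |

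**Does correcting *Unrelated* close the gap?** No. That grade carries the text of *Definitely*, evidently in error. However it is reworded, a plausibly timed event with no better explanation does not belong there, and *Definitely* and *Probably* keep their pattern condition.

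**Is this the only empty cell?** No. Crossing timing (plausible or not) with pattern (known or not) gives 2 × 2 = 4 combinations. Plausible with known leads to *Definitely* or *Probably*. Implausible with unknown leads to *Possibly unrelated*. The other two have no grade when the data are sufficient: the test event, and an implausibly timed event of a known type.

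**Treatment-related tables (SAP 7.1).** Three categories count as related: definite, probable and unclassified. The last is not among the five protocol grades. *Inaccessible* is the nearest match, but neither document says so.
- If the two are the same, an event that the investigator enters as *Inaccessible* is tabulated as related. The test event gets there only if the investigator calls its data insufficient, which by construction they are not.
- If they are not the same, an event entered as *Inaccessible* appears in no treatment-related table.

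**SUSAR route (7.2.7.4).**
- If suspected means graded *Definitely* or *Probably*, a strictly graded reaction of a new type does not qualify, and the sponsor handles it in the annual report.
- If the sponsor judges suspicion independently of the grade, it is expedited.

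The text does not choose between these.

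**What does not depend on the grade.** All SAEs go to the sponsor within 24 hours (7.2.7.1) and to the ethics committee (7.2.7.3), and the investigator reports the SAE to the authorities within 24 hours (7.2.7.4). Only after the last visit does 7.2.2 tie SAE reporting to a causal relationship, although the telephone call in 8.4 collects new SAEs without that condition. TEAEs are tabulated by arm, system organ class, preferred term and maximal severity, and serious TEAEs and TEAEs leading to discontinuation by arm, whatever their causality (Protocol 9.5.2; SAP 7 and 7.1).

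**The case against.** The case against giving this much weight is substantial, and most of it stands.

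- The grades are guidelines applied with judgement, so an investigator may call a new reaction related. True, but a form that needs a grade should offer one that fits, and sites will differ in how literally they read the text.
- The SUSAR rule names no grade, and neither document equates its term unexpected with the absence of a known pattern. So the two sections do not strictly contradict each other. What remains is that the link between grade and suspicion is undefined.
- The SAP's third category may already catch ungradable events. It may, but only through a mapping that is not written down.
- The main safety comparison uses all-causality tables, with no hypothesis test. This stands in full.

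A reader might infer that the SUSAR rule and the related tables can never capture an unexpected reaction. The first three points show that the documents do not support that.

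A reader might also take the US study as a measure of the problem, since Protocol 1.4.2 says "The most common unexpected ocular TEAEs related to the study drug were installation site pain and allergic conjunctivitis" and reports 8 withdrawals for allergic conjunctivitis (3 on 0.10%, 5 on 0.25%). It is not one. The causality scale used there is not given; the events were in fact classed as related; no SAEs occurred, so nothing follows about missed SUSARs; and both event types are now described in this protocol, so here they count as known.

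**Conclusion.** The gap is real but limited. As printed, 7.2.4 has no positively related grade for a well-documented, plausibly timed reaction of a new type, and read literally it has no grade for it at all. Two things then rest on unstated conventions: entry into the treatment-related TEAE tables, and whether the sponsor treats a serious case as suspected or leaves it to the annual report.

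This rests on reading the listed conditions as required rather than illustrative, and on sites following them. The number of events affected cannot be estimated from the documents. The exposed outputs are the two treatment-related tables and the sponsor's expedited report. SAE reporting to the sponsor, ethics committee and authorities during treatment, the all-causality tables and the efficacy analysis are not touched. The wording should be corrected because a stated rule, followed as written, misgrades a foreseeable kind of event and the repair is cheap.

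**What to change.** 1. **Protocol 7.2.4.** Make the known response pattern supportive evidence rather than a condition, so that an event with plausible timing and no better alternative explanation can receive a related grade whether or not its type has been seen before. Do not do this by sending such events to *Probably* as now worded, because that grade presupposes another reasonable explanation. Revise the grades together with the duplicated *Unrelated* text, so that every combination of timing, pattern and alternative explanation has one grade.
2. **Protocol 7.2.7.4.** State that expectedness is judged separately from causality, and list the grades that count as suspected.
3. **SAP 7.1.** Replace *unclassified* with the protocol's grade name.

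The cost is wording in both documents and a note in site training; no new data are needed. The downside is somewhat more events counted as related and possibly a few more expedited reports.
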